5. PRECLINICAL EXPERIENCE WITH THE STUDY DRUG

5.1. Acute Tox study - old formulation ArtemiC

Each group 3M+3F rat were treated in splash route of administration of ArtemiC (6 mg/ml of Artemisinin ,10 mg/ml curcumin and 7.5 mg/ml Boswellia) into the oral cavity on day 1 with the experimental substances t according to the group table. Each animal was weighed prior to treatment.

Study groups:

Group 1 (n=3M + n=3F): 50ul saline per rat

Group 2 (n=3M + n=3F): 48ug ArtemiC / per Kg rat

Group 3 (n=3M + n=3F): 96ug ArtemiC / per Kg rat

Group 4 (n=3M + n=3F): 192ug ArtemiC / per Kg rat

	MGC Pharma Clinical Study Protocol	Protocol No.: MGC-009
		Version 02, 05 Sep 2021
		Page 19 of 76
A Phase IIb, double blind, placebo-controlled clinical study designed to evaluate the effect of CimetrA in patients diagnosed with COVID-19		CONFIDENTIAL

During all 7 days of the experiment the animals were monitored for observation and weight to detect the appearance of abnormal clinical signs. No clinical signs were observed in the animals. No blood tests or histopathology abnormalities were observed.

The full Acute Tox Report is be presented in the Investigator Brochure.

5.2. In Vitro Mechanism of Action trial

The study included 2 main stages –

- Viability evaluation of PBMCs
- Examination of anti-inflammatory effect

Conclusions of the study included –

- Treatment of PBMCs with ArtemiC and its components allowed preservation of PBMCs viability and did not lead to cytotoxic effect. The results are presented in Fig. 1-4.

	MGC Pharma Clinical Study Protocol	Protocol No.: MGC-009
		Version 02, 05 Sep 2021
		Page 20 of 76
A Phase IIb, double blind, placebo-controlled clinical study designed to evaluate the effect of CimetrA in patients diagnosed with COVID-19		CONFIDENTIAL

[figure not shown]

Fig. 1. PBMCs viability after treatment by ArtemiC and its components in different combinations.

- Pre-treatment of PBMCs with ArtemiC and its components resulted in attenuation of cytokines related to COVID-19 elevation following LPS stimulation. The results are presented in figures 3-5.

One of the goals of this study was to determine the most effective compounds combination in order to define the final formulation. Based on the results, Artemisinin was taken out of the formulation , the new formulation which was chosen is CimetrA : a combination of curcumin and Bowsellia

	MGC Pharma Clinical Study Protocol	Protocol No.: MGC-009
		Version 02, 05 Sep 2021
		Page 21 of 76
A Phase IIb, double blind, placebo-controlled clinical study designed to evaluate the effect of CimetrA in patients diagnosed with COVID-19		CONFIDENTIAL

[figure not shown]
[figure not shown]

Fig. 2. TNF-α concentration in PBMCs conditioned medium samples after treatment with ArtemiC and its components in different combinations, include the combination of CimetrA .

	MGC Pharma Clinical Study Protocol	Protocol No.: MGC-009
		Version 02, 05 Sep 2021
		Page 22 of 76
A Phase IIb, double blind, placebo-controlled clinical study designed to evaluate the effect of CimetrA in patients diagnosed with COVID-19		CONFIDENTIAL

Fig. 3. IL-6 concentration in PBMCs conditioned medium samples after treatment with ArtemiC and its components in different combinations, include the combination of CimetrA .

[figure not shown]

Fig. 4. IL-1Ra concentration in PBMCs conditioned medium samples after treatment with ArtemiC and its components in different combinations, include the combination of CimetrA . Full report is submitted in the Investigator Brochure.

5.3. Efficacy Animal Model Study

Evaluation the efficacy ofArtemiC treatment in ARDS model in mice. The goal of this study is to investigate the efficacy of ArtemiC in the ARDS model in mice by Oral Spray administration in two dosage. Use of animals in ARDS model enabled to test the efficacy of ArtemiC for the inhibition of clinical symptoms, base of the inflammatory response, and will be enable further development of this treatment for

	MGC Pharma Clinical Study Protocol	Protocol No.: MGC-009
		Version 02, 05 Sep 2021
		Page 23 of 76
A Phase IIb, double blind, placebo-controlled clinical study designed to evaluate the effect of CimetrA in patients diagnosed with COVID-19		CONFIDENTIAL

ARDS. The LPS-induced ARDS model is an accepted model for human acute respiratory disease caused by Corona virus infection.

The study investigated the levels of cytokines and chemokines in blood and BALF (bronchoalveolar lavage fluid). Inflammation level of the lung tissue was measured by histopathology.

ArtemiC was found effective in the reduction of elevation of cytokines and chemokines production both in blood and BALF. The histopathological analysis demonstrated the attenuation of the lung injury in the treatment group in comparison with placebo.

The detailed study result information is provided in the Investigator Brochure.

6. **CLINICAL EXPERIENCE WITH THE STUDY DRUG -THE OLD FORMULTION- ARTEMIC**

Randomized controlled Phase II clinical trial was managed on 50 moderate COVID-19 patients in Israel (40 patients were recruited) and India (10 patients) to measure safety and efficacy of ArtemiC.

Patients were randomized 2:1.

Study drug: ArtemiC was administrated in the dosage of Artemisinin 12 mg, Curcumin 40 mg, Boswellia 30 mg and Vitamin C 120 mg, in spray administration – divided in 4 separate doses given as an add on therapy, 4 doses over 48 hours (day 1 and day 2), twice a day (morning and evening). The study drug dose was defined based on the Acute Tox preclinical study.

Main demographic characteristics are presented in Table 1.

	MGC Pharma Clinical Study Protocol	Protocol No.: MGC-009
		Version 02, 05 Sep 2021
		Page 24 of 76
A Phase IIb, double blind, placebo-controlled clinical study designed to evaluate the effect of Cimetra in patients diagnosed with COVID-19		CONFIDENTIAL

Table 1. Demographic characteristics of patients in Phase II study.

	ArtemiC	Placebo	P
Age	52± 14	53± 14	0.857
Gender:			

7. FORMULATION CHANGE

Artemisinin was excluded from the finished product due to insufficient compatibility with other active ingredients. Artemisinin has shown poor stability in low pH water

	MGC Pharma Clinical Study Protocol	Protocol No.: MGC-009
		Version 02, 05 Sep 2021
		Page 29 of 76
A Phase IIb, double blind, placebo-controlled clinical study designed to evaluate the effect of CimetrA in patients diagnosed with COVID-19		CONFIDENTIAL

environment, what is caused by the API boswellic acids and antioxidant vitamin C.

This decision is supported by the preclinical data of the in vitro tests of **CimetrA** and its compounds in different combinations, presented in the section of Preclinical experiments of the IB. The analysis of the formulation ultimately clarified that the artemisinin component with which it was formulated was unstable to the extent that neither it, nor its metabolites were present in the preparations used in the phase II trial.

As a part of the development process for the multi APIs medical products, the Sponsor continue the preclinical program and based on the in vivo preclinical study, presented in Section 4.2 of the Investigator Brochure, performed additional preclinical trials in the new formulation, named CimetrA, which does not include Artemisinin.

The in vitro trial aimed to check the anti-inflammatory activity of ArtemiC (Artemisinin, Boswellia, Vitamin C, Curcumin) versus CimetrA (Boswellia, Curcumin) in the related to COVID-19 cytokines and chemokines was performed in Science in Action Lab, Ness Ziona, Israel.

The objective of this study was to examine the effect of ArtemiC and CimetrA on human peripheral blood mononuclear cells (PBMCs) viability and their capacity to attenuate inflammatory response upon stimulation with E coli-derived lipopolysaccharide (LPS).

The study demonstrated the superiority of the formulation named CimetrA (based on Curcumin and Boswellia) on ArtemiC (based on Artemisinin, Curcumin, Boswellia and vitamin C) in the prevention of uncontrolled COVID-19 related cytokines and chemokines production.

The results are presented below.

	MGC Pharma Clinical Study Protocol	Protocol No.: MGC-009
		Version 02, 05 Sep 2021
		Page 30 of 76
A Phase IIb, double blind, placebo-controlled clinical study designed to evaluate the effect of Cimetra in patients diagnosed with COVID-19		CONFIDENTIAL

[figure not shown]

Fig 6. Concentration of TNF-alpha in PBMCs supernatant

[figure not shown]

Fig 7. Concentration of IL-18/IL-1F4 in PBMCs supernatant

	MGC Pharma Clinical Study Protocol	Protocol No.: MGC-009
		Version 02, 05 Sep 2021
		Page 31 of 76
A Phase IIb, double blind, placebo-controlled clinical study designed to evaluate the effect of CimetrA in patients diagnosed with COVID-19		CONFIDENTIAL

[figure not shown]

Fig 8. Concentration of IL-6 in PBMCs supernatant

[figure not shown]

Fig 9. Concentration of CXCL10/IP-10/CRG-2 in PBMCs supernatant

	MGC Pharma Clinical Study Protocol	Protocol No.: MGC-009
		Version 02, 05 Sep 2021
		Page 32 of 76
A Phase IIb, double blind, placebo-controlled clinical study designed to evaluate the effect of Cimetra in patients diagnosed with COVID-19		CONFIDENTIAL

[figure not shown]

Fig 10. Concentration of CCL2/JE/MCP-1 in PBMCs supernatant

Based on the data presented above, MGC Pharma decided to continue the clinical program (phase IIb) with more active formulation, Cimetra, which answers all the goals of the cytokine storm prevention in COVID-19 patients needs. This formulation is developed and manufactured under EU-GMP conditions and certificates in the EU-certified manufacturing facility of MGC Pharma.

	MGC Pharma Clinical Study Protocol	Protocol No.: MGC-009
		Version 02, 05 Sep 2021
		Page 33 of 76
A Phase IIb, double blind, placebo-controlled clinical study designed to evaluate the effect of Cimetra in patients diagnosed with COVID-19		CONFIDENTIAL

8. STUDY OBJECTIVES

This study designed to evaluate the efficacy, pharmacokinetic parameters and safety of Cimetra on patients diagnosed with COVID-19.

9. STUDY ENDPOINTS

9.1. The primary outcomes:

- **Efficacy endpoint**

- 1- Change in WHO Ordinal Scale for clinical improvement (baseline to end of study will be measured on days 1,7,14 and 28).

The World Health Organization (WHO-WHO) has proposed the “Ordinal Scale of Clinical Evaluation of the World Health Organization” presented below as a means of generating a numerical value to assess the health status of the participant to allow comparisons to be made in clinical studies. The scale is shown in the table below and will be used to assess a secondary effectiveness target in this study.

Patient State	Descriptor	Score
Uninfected	Uninfected; no clinical evidence and viral RNA detected	0
Ambulatory	Symptomatic; independent	1
	Symptomatic; assistance needed	2
Hospitalized: Moderate diseases	Hospitalized, no oxygen therapy	3
	Hospitalized; oxygen by mask or nasal prongs	4

	MGC Pharma Clinical Study Protocol	Protocol No.: MGC-009
		Version 02, 05 Sep 2021
		Page 34 of 76
A Phase IIb, double blind, placebo-controlled clinical study designed to evaluate the effect of CimetrA in patients diagnosed with COVID-19		CONFIDENTIAL

Hospitalized: Severe diseases	Hospitalized; oxygen by NIV or high flow	5
	Hospitalized; mechanical ventilation	6
	Mechanical ventilation and vasopressors, dialysis or ECMO	7
Dead	Dead	8

2- Change in COVID-19-Related Symptoms score (measured on days 1,7, 14, 28)

• **Safety Endpoints**

Safety will be assessed through collection and analysis of adverse events, blood and urine laboratory assessments and vital signs.

9.2. **The secondary outcomes:**

- Number of participants with depending on oxygen supplementation through day 28 since onset of symptoms
- Change in inflammatory marker levels - IL-6, IL-1 β , IL-12, TNF α , IFN- γ , CRP, NLR (Neutrophil / Lymphocyte ratio) (days 1, 2, 4, 7) compared to baseline
- Pharmacokinetic profile of the study drug on day 1 through 24 Hrs.
- Incidence and duration of mechanical ventilation
- Incidence of Intensive Care Unit (ICU) stay during COVID-19 complication
- Percentage of participants with definite or probable drug related adverse events
- Long term adverse events of COVID-19 on Day 28
- The Impact covid_19 on quality of life of patients on Days 1, 14 and 28

9.3. **The exploratory outcomes:**

- Course of change in D Dimer levels compared to baseline

	MGC Pharma Clinical Study Protocol	Protocol No.: MGC-009
		Version 02, 05 Sep 2021
		Page 35 of 76
A Phase IIb, double blind, placebo-controlled clinical study designed to evaluate the effect of CimetrA in patients diagnosed with COVID-19		CONFIDENTIAL

- Occurrence of secondary infections

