10. STUDY DESIGN AND PROCEDURES

240 adult patients who suffer from COVID-19 infection and do not participate in any other clinical trial. Patient must not agree to participate in any new clinical study during the study duration. Study will take place during patient's hospitalization due to COVID-19 infection. The study will last up to 4 weeks, until conclusion on day 28. In case of hospital discharge within the study period, follow up will continue per protocol until day 28 wherever the subject will be located, depending on the status of the patient and study schedule.

If patient discharged, visits will be performed via phone call, if he still hospitalized, visits will be performed at corona department.

Only on day 28, all the patients must undergo clinic visit, they will arrive to the research clinic (only patient who will be under quarantine will have a phone call visit).

The study is not designed to include participants from a special population, so that patients with mental and intellectual problems, lack of judgment, children under the age of 18 and pregnant women will not be allowed to participate, or any patient who have a legal guardian.

Standard of care treatment acceptable to be used while patient participates in study:

Treatment will include:

Supportive care - symptomatic

Painkillers

Anticoagulant therapy

	MGC Pharma Clinical Study Protocol	Protocol No.: MGC-009
		Version 02, 05 Sep 2021
		Page 36 of 76
A Phase IIb, double blind, placebo-controlled clinical study designed to evaluate the effect of CimetrA in patients diagnosed with COVID-19		CONFIDENTIAL

Steroids

REMDESIVIR - Compassionate treatment

Antibiotic treatment as needed

Inhalations if necessary

Oxygen

The treatments offered above are given according to the guidelines of the Ministry of Health.

The treatment will be given to the patient according to the clinical judgment of the medical staff and in accordance with the patient's health condition, and therefore the treatment does not have to be the same in each of the medical centers participating in the study.

10.1. **Enrollment**

Each candidate subject will be reviewed for an inclusion/exclusion criteria. After signing the ICF, the candidate subject will be asked to provide a medical history and undergo a physical examination, including measurement of blood pressure, pulse, temperature (PO), body weight and height, saturation, respiratory rate, vas scale, news score.

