10.2. Trial entry and enrollment: Medication schedule

Study drug will be administrated twice a day during days 1 and 2. Patients will be monitored for adverse events.

10.2.1. Clinical and laboratory follow up:

Subjects will be followed through regularly scheduled visits that will include: vital signs, physical examination, ongoing medical history review, and laboratory tests as described in Table 5.

Safety will be assessed by monitoring the subjects for AEs. The subjects will be instructed as to what is an AE and will be requested to fill out a diary detailing any AEs that may occur during the time period between visits.

Evaluation of the effect of oral administration of the study drug will be assessed by determining the clinical and laboratory tests as summarized below.

	MGC Pharma Clinical Study Protocol	Protocol No.: MGC-009
		Version 02, 05 Sep 2021
		Page 38 of 76
A Phase IIb, double blind, placebo-controlled clinical study designed to evaluate the effect of CimetrA in patients diagnosed with COVID-19		CONFIDENTIAL

Table 5: Schedule of events

Day	1	2	3-6	7	8-13	14	Day 21(phone visit)	Day 28 Clinic visit
Confirmed SARS-CoV-2 infection	X					X		X
Treatment administration (twice a day)	X	X						
Inclusion/Exclusion criteria evaluation	X							
Informed Consent	X							
Medical History	X							
Concomitant Medications	X	X	X	X	X	X	X	X
AE Assessment		X	X	X	X	X	X	X
Randomization	X							
Physical Examination	X	X	X	X	X	X		X
Vital Signs	X	X	X	X	X	X		X
Hematology blood test (local)	X	X	X**	X	X**	X		X
Biochemistry blood test (local)	X	X	X**	X	X**	X		X
WHO Ordinal Score	X			X		X	X	X
COVID-19-Related Symptoms assessment	X			X		X	X	X
PK test*	X							
Blood test for inflammatory markers (IL-6, IL-1 β , IL-12, TNF α , IFN- γ) (local)	X	X	X	X		X		X

	MGC Pharma Clinical Study Protocol	Protocol No.: MGC-009
		Version 02, 05 Sep 2021
		Page 39 of 76
A Phase IIb, double blind, placebo-controlled clinical study designed to evaluate the effect of Cimetra in patients diagnosed with COVID-19		CONFIDENTIAL

D-Dimer test (local)	X	X		X		X		X
VAS scale	X	X	X	X	X	X	X	X
Urine pregnancy test for women of childbearing potential	X							X
ECG	X							x
COVID-19–Impact on Quality of Life Questionnaire	X			X	X	X	X	X
POST- COVID-19 Functional Status Scale								X

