Time point 10	10 h post dose

	MGC Pharma Clinical Study Protocol	Protocol No.: MGC-009
		Version 02, 05 Sep 2021
		Page 41 of 76
A Phase IIb, double blind, placebo-controlled clinical study designed to evaluate the effect of Cimetra in patients diagnosed with COVID-19		CONFIDENTIAL

Time point 11	12 h post dose
---------------	----------------

Day 1

Prior to engaging in any study procedures, the subject must meet the inclusion/exclusion criteria by history (which includes a signed declination), and review and sign an ICF.

Following procedures will be performed during the visit –

- Inclusion/Exclusion criteria evaluation
- Informed Consent
- Medical History
- Concomitant Medications
- Physical Examination
- Vital Signs
- Hematology blood test (local, mandatory even if there are available results from the day before)
- Biochemistry blood test (local, mandatory even if there are available results from the day before)
- PCR test for detection COVID-19 (within 5 days from admission to hospital)
- COVID-19-Related Symptoms Assessment
- WHO Ordinal scale
- Blood test for inflammatory markers (IL-6, IL-1 β , IL-12, TNF α , IFN- γ) (local)
- D-Dimer test (local)
- VAS scale
- Urine pregnancy test for women of childbearing potential
- ECG
- COVID-19–Impact on Quality of Life Questionnaire

	MGC Pharma Clinical Study Protocol	Protocol No.: MGC-009
		Version 02, 05 Sep 2021
		Page 42 of 76
A Phase IIb, double blind, placebo-controlled clinical study designed to evaluate the effect of CimetrA in patients diagnosed with COVID-19		CONFIDENTIAL

- Randomization in 1:1:1 ratio to study drug (CimetrA-1) (Arm 1) or study drug (CimetrA-2) or to Placebo (Arm 3)
- Treatment administration (twice a day, morning, and evening)
- **PK test (only for Brazil and South Africa)** for first dose of the drug (5 puffs) as the table on page 36, PK must be done **before** receiving standard of care.

Day 2

- Concomitant Medications
- AE Assessment
- Physical Examination
- Vital Signs
- Hematology blood test (local, mandatory even if there are available results from the day before)
- Biochemistry blood test (local, mandatory even if there are available results from the day before)
- Blood test for inflammatory markers (IL-6, IL-1 β , IL-12, TNF α , IFN- γ) (local)
- D-Dimer test (local)
- VAS scale
- Treatment administration (twice a day, morning and evening)

Days 3-6

- Concomitant Medications
- AE assessment
- Physical Examination
- Vital Signs

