11. STUDY POPULATION

11.1. Inclusion Criteria:

1. Confirmed by PCR test SARS-CoV-2 infection (according to nationally authorized laboratory criteria).
2. Hospitalized patient with COVID-19 of moderate stable or worsening severity not requiring ICU admission (defined by NIH criteria - fever, cough, dyspnea, fast breathing, but no signs of severe pneumonia, including SpO₂ ≥ 94% on room air).
3. Age: 18 years old and above.
4. Subjects must be hospitalized
5. Ability to receive treatment by spray into the oral cavity

	MGC Pharma Clinical Study Protocol	Protocol No.: MGC-009
		Version 02, 05 Sep 2021
		Page 47 of 76
A Phase IIb, double blind, placebo-controlled clinical study designed to evaluate the effect of CimetrA in patients diagnosed with COVID-19		CONFIDENTIAL

11.2. Exclusion Criteria:

1. Tube feeding or parenteral nutrition.
2. Patients with scores 5 or above per the Ordinal Scale for Clinical Improvement published by the WHO. (i.e., who need oxygen supply beyond use of nozzles or simple mask)
3. Need for admission to ICU while of the present hospitalization at any time prior to completion of the recruitment to the study.
4. Any condition which, in the opinion of the Principal Investigator, would prevent full participation in this trial or would interfere with the evaluation of the trial endpoints.

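### The secondary oxygen endpoint is timed from symptom onset while the trial runs on study days, so its window opens before randomisation and closes on a different study day for each patient

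*Protocol*

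**What the plan says.** Protocol section 9.2 and the synopsis define the outcome in the same words: "Number of participants with depending on oxygen supplementation through day 28 since onset of symptoms".

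The rest of the trial keeps a different clock. Section 10 says "The study will last up to 4 weeks, until conclusion on day 28". Section 10.2 puts randomisation under Day 1 and states "Study drug will be administrated twice a day during days 1 and 2". Table 5 schedules the WHO Ordinal Score on study Days 1, 7, 14, 21 and 28.

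On entry, section 11.1 requires "Hospitalized patient with COVID-19 of moderate stable or worsening severity not requiring ICU admission", with a room-air saturation of at least 94% in the same criterion. Section 11.2 excludes "Patients with scores 5 or above per the Ordinal Scale for Clinical Improvement published by the WHO", glossed as patients "who need oxygen supply beyond use of nozzles or simple mask". In the scale printed in section 9.1, score 4 is "Hospitalized; oxygen by mask or nasal prongs". None of the five inclusion and four exclusion criteria limits the time since symptom onset.

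**The concern.** In a randomised comparison an outcome window should start at randomisation, because nothing before that point can be affected by treatment. Here the window starts earlier, by a lag that differs between patients, is not capped at entry and rests on a history-based onset date. Two things follow on an 'ever on oxygen' reading:

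- Oxygen that began and ended before the first dose can count as an event in any arm.
- The window closes before study Day 28, so later oxygen use is left out although the patient is still being followed.

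At stake are a diluted difference between arms and lost information on a clinically readable secondary outcome.

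**Working it through.** **The plan's own figure.** No rate, effect or power is stated for the oxygen outcome. The sample size in section 17 concerns the WHO scale only: with f = 0.20, N = 240 and three groups, λ = 240 × 0.04 = 9.6 on 2 and 237 degrees of freedom gives power 0.793. That is just under the stated 80%, which needs 82 per arm. The oxygen endpoint does not affect this.

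**Step 1: the window left after randomisation.** Let d be the days from onset to randomisation. The documents give no distribution for d, so the values below are assumptions. Counting onset as day 1, day 28 since onset is study day 28 − d. Counting onset as day 0 moves this one day later.

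| d (assumed) | 28 − d | share of 28 days |
|---|---|---|
| 3 | 25 | 89% |
| 5 | 23 | 82% |
| 7 | 21 | 75% |
| 10 | 18 | 64% |
| 14 | 14 | 50% |

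These are calendar days, not events. Oxygen that starts in the last d study days is not counted.

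**Step 2: the other reading.** If the outcome means still dependent on oxygen at day 28, the target date is study day 23 or 24 for d = 5, and 18 or 19 for d = 10. These lie between the WHO scores on Days 21 and 28, and on Days 14 and 21. The date meets a scheduled score only by chance, for example at d = 7 or 14 with onset as day 1.

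**Step 3: what the onset anchor changes.** On the 'ever' reading, compare counting from onset with counting from randomisation:

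- Added by the onset anchor: patients whose oxygen started and stopped before Day 1 and who need none afterwards.
- Lost by it: patients whose first oxygen use falls after day 28 since onset but by study Day 28.
- Unchanged: patients on oxygen on Day 1, who count under either anchor.

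The documents give neither the added nor the lost share, so the net effect cannot be calculated.

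**Step 4: oxygen at entry, a separate issue.** Let b be the share on oxygen at entry and p the risk of new oxygen use in the rest. The observed risk is b + (1 − b)p, and the difference between arms is multiplied by (1 − b). With assumed risks of 30% and 15%:

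- b = 0: 30% v 15%, 15 points.
- b = 0.2: 0.2 + 0.8 × 0.30 = 44% v 0.2 + 0.8 × 0.15 = 32%, 12 points.
- b = 0.4: 58% v 49%, 9 points.
- b = 0.6: 72% v 66%, 6 points.

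With 80 per arm, pairwise power is 0.62, 0.35 and 0.21 for b = 0, 0.2 and 0.4. Moving the anchor alone would change none of these figures. They show what it costs to pool patients already on oxygen with those at risk of starting it.

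**The case against.** The strongest reply is that this is one of eight secondary outcomes. Section 17 rests study success on the WHO-scale hypothesis alone, and allocation is randomised, stratified by centre and double-blind, so lags should balance across arms. All of that stands, and it limits the point to efficiency and clarity.

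It can also be said that the wording is ambiguous. If it describes a persisting state, oxygen that ended before the first dose is not an event. That is correct, but Step 2 shows that this reading then has a target date that generally misses the scheduled assessments. A third possibility, that study day 28 was meant, is contradicted by the phrase about symptom onset, which appears in both places.

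Some stronger inferences are tempting but not supported:

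- A reader might infer that total follow-up for this outcome differs between patients. It is 28 days from onset for everyone; only the part after randomisation varies.
- A reader might put the shrinkage from 15 to 12, 9 or 6 points down to the onset anchor. It comes from score-4 eligibility. The room-air saturation criterion also weighs against the larger assumed shares, although it does not exclude oxygen given earlier in the illness.
- A reader might say that every other endpoint is counted from Day 1. The ventilation and ICU outcomes state no time origin.
- A reader might say that collected data are thrown away. The WHO score is still recorded to Day 28 and feeds the primary endpoint.

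**Conclusion.** The point holds in a limited form. As written, the window opens before randomisation and closes on a patient-specific study day, and no other text in the protocol repairs this. The post-randomisation window is 23 to 18 days for an assumed lag of 5 to 10 days, and 25 to 14 days for 3 to 14. The resulting dilution and loss of information cannot be sized, because the documents give neither the lag nor the share of patients whose oxygen ended before Day 1. No arm is systematically favoured, and the primary analysis is untouched.

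The eligibility text raises a second, separate question. Exclusion criterion 2 admits score 4, while inclusion criterion 2 asks for at least 94% saturation on room air. The passages must be reconciled. Until they are, the share on oxygen at entry is unknown, and the figures in Step 4 are illustrations on assumed shares and risks. The change is worth making, at the priority of a secondary endpoint.

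**What to change.** In section 9.2 and the synopsis, define the outcome from randomisation (study Day 1) through study Day 28. Count new supplemental oxygen use among patients not on oxygen at baseline. For patients on oxygen at baseline, report separately the number still on oxygen at Day 28. Take the data from the WHO score on Days 1, 7, 14, 21 and 28 and from the concomitant-treatment record in section 13. Separately, the sponsor should reconcile inclusion criterion 2 with exclusion criterion 2 on oxygen at entry.

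The cost is a rewording of one outcome in two places, and the outcome no longer depends on a recalled onset date. There are two drawbacks. Table 5 has no oxygen-use item, so use that starts and stops between WHO scores is seen only if the concomitant-treatment record captures oxygen completely; it should not be assumed that nothing extra needs collecting. Splitting by baseline oxygen also leaves fewer than 80 patients per arm in the new-use comparison if some are on oxygen at entry.
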